#### 2 STUDY OBJECTIVES

#### 2.1 PRIMARY OBJECTIVE

The primary objective is to determine the efficacy of RUX and FOS to reduce the proportion of hospitalised patients progressing from mild/moderate to severe COVID-19 pneumonia. A modified WHO COVID-19 Severity Ordinal Scale (COVID-19 Therapeutic Trial Synopsis published 18th February 2020) will be used to grade clinical deterioration from Hospitalised Mild Disease (<5) to Hospitalised Severe Disease (≥ 5). The modification includes an additional grade for Hospitalised Severe Disease that allows the capture of clinical deterioration in patients for whom escalation in organ support is not offered. Patients are eligible for recruitment to MATIS at grades 3 or 4. These patients stand to gain the greatest benefit from inflammatory signal inhibitors that may ameliorate the cytokine storm and prevent organ failure.

Table 1. Modified WHO COVID-19 Severity Scale, from the WHO R&D Blueprint

Patient state Descriptor		Grade
Uninfected	No clinical or virological evidence of infection	0
Ambulatory	No limitation of activities	1

MATIS version 4.0 dated 2nd November 2022

IRAS: 282552 Page **20** of **57** 

	Limitation of activities	2
Haspitalisad mild disease	Hospitalised, no oxygen therapy	3
Hospitalised mild disease	Oxygen by mask or nasal prongs	4
	$SpO_2$ < 90% on $FiO_2$ $\geq$ 60% by face mask	5
Hospitalised severe disease	Non-invasive ventilation, CPAP or high-flow oxygen	6
	Intubation and mechanical ventilation	7
	Ventilation + additional organ support (vasopressors, RRT, ECMO)	8
Dead	Death	9

Published in the COVID Therapeutic Trial Synopsis, February 18th 2020

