In Stage 2 a logistic regression model will be used to assess the treatment effect of RUX and FOS compared to SOC. The model will include the treatment arms, baseline modified WHO Severity Score, trial co-enrolment at baseline, and randomisation stratification variables viz. site and age (<65 vs ≥65). As well as reporting OR and 95% CIs, the model will be used to estimate the difference in proportion of participants with modified WHO COVID-19 Ordinal Score ≥5. The treatment effect in the absence of post-randomisation co-enrolment and receipt of rescue medication will be estimated in a supplementary analysis where participants' outcomes after either will be treated as missing and a controlled multiple imputation using a delta based approach will be used.

For the primary outcome, progression to severe COVID-19 disease within 14 days, discharge alive from the admitting hospital before 14 days will assume safety from the event (in the absence of additional data confirming otherwise). An additional sensitivity analysis will be performed if there is a change of dose after review of the first thirty patients.

For time-to-event analyses required for secondary endpoints such as time to discharge, each treatment group will be compared with SOC and modelled using a proportional hazards time-to-event model adjusted for randomisation stratification variables. Kaplan-Meier estimates for the time to event will also be plotted (with confidence intervals). The log-rank 'observed minus expected' statistic (and its variance) will be used to estimate the average event rate ratio (and its confidence interval) for those allocated to each treatment group versus the no additional treatment group.

Pre-specified subgroup analysis will be conducted for the primary outcome using the statistical test for interaction (or test for trend where appropriate) for the following: disease severity as graded by the WHO

MATIS version 4.0 dated 2nd November 2022

IRAS: 282552 Page **28** of **57** 

Imperial College Healthcare

COVID-19 Ordinal Severity Scale; time since onset of symptoms; sex; age; and comorbidities obesity, chronic heart, lung, kidney and liver disease, diabetes, immunocompromised and smoking status. Pre-specified subgroup analyses will also be conducted for the primary outcome using the statistical test for interaction (or test for trend where appropriate) for patients with admission CRP >200mg/L and/or D-dimer 2500ng/mL.

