1.8 Brief description of proposed analysis

Efficacy analysis population: We will use the intention-to-treat (ITT) population which includes all randomised participants analysed in the treatment arm to which they were allocated to regardless of treatment subsequently received, multiple imputation will be used to account for any missing data such that all randomised participants are included in the final analysis. At the formal interim analysis multiple imputation will be undertaken if greater than 5% of outcome data are missing, if \leq 5% missing a complete case analysis will be undertaken.

Safety analysis population: We will include participants who received at least one dose of study medication and analysis will be according to treatment received, regardless of randomised treatment assignment.

The formal interim analysis will be conducted after 171 participants have been recruited and have completed 14 days of follow-up after randomisation. If an experimental treatment is recommended to continue an additional 95 participants will be recruited for each arm that continues and final analysis will be completed after all participants have completed 28 days of follow-up after randomisation.

Formal interim and final analyses will be carried out sub-group blind and follow the ITT principle. That is, all randomised patients will be analysed in the treatment arm to which they were allocated to regardless of treatment subsequently received, multiple imputation will be used to include all randomise participants for the final analysis, at the formal interim analysis multiple imputation will be undertaken if greater than 5% of outcome data are missing. The analysis of the serious adverse events will be undertaken on the safety population.

All regression analysis will include adjustment for age group (<65 years or ≥65 years) and site where appropriate, since these were stratification factors in the randomisation.

All confidence intervals will be presented at the 95% level.

For the formal interim analysis (stage 1) one-sided p-values \leq 0.25 will indicate that an experimental treatment should be recommended to continue to stage 2 and for the final (stage 2) analysis one-sided p-value \leq 0.027 will be interpreted as statistically significant for the primary outcome.

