The stage two primary analysis will consist of fitting one binomial regression model regardless of whether one or two experimental treatments progress from stage one. Specifically a generalized linear model with WHO COVID-19 status (<5 or \ge 5) as the outcome and treatment group, baseline WHO COVID-19 score (3 or 4), age (<65 or \ge 65), receipt of known effective treatments dexamethasone and/or tociluzimab, prior vaccination against COVID-19 (y/n) and receipt of paxlovid and/or molnupiravir at the time of or prior to randomisation into MATIS as covariates will be fitted. Effective treatments will be included as separate covariates in the primary analysis model. Given the anticipated small number of sites in this study, site will also be included in the model as a fixed effect. In the event that all participants are on one of the effective treatments that covariate will be removed from the model.

If including site as a fixed effect results in unstable model estimates e.g. if there are a number of sites with very few randomisations we will exclude site from the model and we will only adjust for baseline WHO COVID score, age group, receipt of known effective treatments dexamethasone and/or tociluzimab, prior vaccination against COVID-19, and receipt of paxlovid and/or molnupiravir.⁶ We will also consider not adjusting for paxlovid and/or molnupiravir if the number of participants receiving these are low. If after removing sites and treatments the model is not stable due to event rate:covariate ratio we will adjust for all covariates using a propensity score approach.

The model will be fitted with a binomial distribution and logit link function and the treatment effect will be reported as an odds ratio with corresponding 95% confidence interval and p-values. P-values will be one-sided and judged at the 0.027 level. Therefore, a two-sided p-value < 0.054 will be used to indicate a significant treatment effect.

The stage two model to be fitted to estimate the treatment effects will be:

$$logit(\pi_{ij}) = \beta_{0} + \beta_{1}RUX_{ij} + \beta_{2}FOS_{ij} + \beta_{3}WHO_{ij}^{0} + \beta_{4}AGE_{ij}^{0} + \beta_{5}DEX_{ij}^{0} + \beta_{6}TOC_{ij}^{0} + \beta_{7}VAC_{ij}^{0} + \beta_{8}PAX_{ij}^{0} + \beta_{9}MOL_{ij}^{0} + \beta_{10}SITE_{1} + \beta_{11}SITE_{2} + \cdots + \beta_{12}SITE_{i-1}$$

 RUX_{ij} : dummy variable for treatment ($RUX_{ij} = 0$ or 1) for participant i in jth site

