3.2.2 Modified WHO COVID-19 score

A mixed effects ordered logistic regression will be used to estimate the odds ratio of disease severity as measured by the modified WHO COVID-19 (ordinal scale) over time by treatment arm. Specifically a generalized linear model with modified WHO COVID-19 status (scores 3/4 through to 9) as the outcome (ordered categorical variable) with S ordinal categories s (s=3/4, 5, 6, 7, 8, 9) and treatment group, time, time-by-treatment arm interaction, baseline WHO COVID-19 score (3 or 4), age (<65 or \geq 65), receipt of known effective treatments dexamethasone and/or tociluzimab, prior vaccination against COVID-19, and receipt of paxlovid and/or molnupiravir at the time of or prior to randomisation into MATIS as covariates will be fitted. Participants will be included as a random intercept (ζ_{ij}). Given the anticipated small number of sites in this study, site will be included in the model as a fixed effect. The model will be fitted using the *ologit* link function (or the *meologit* command) in Stata and the treatment effect will be reported as an odds ratio with corresponding 95% confidence intervals.

The model to be fitted will be:

$$\begin{split} logit \big(pr(\pi_{ij} > s) \big) \\ &= \beta_1 RUX_{ij} + \beta_2 FOS_{ij} + \beta_3 WHO_{ij}^0 + \beta_4 AGE_{ij}^0 + \beta_5 DEX_{ij}^0 + \beta_6 TOC_{ij}^0 \\ &+ \beta_7 VAC_{ij}^0 + \beta_8 PAX_{ij}^0 + \beta_9 MOL_{ij}^0 + \beta_{10} SITE_1 + \beta_{11} SITE_2 + \cdots \\ &+ \beta_{12} SITE_{j-1} + \beta_{13} time_7 + \beta_{14} time_{14} + \beta_{15} RUX_{ij} * time_7 + \beta_{16} RUX_{ij} \\ &* time_{14} + \beta_{17} FOS_{ij} * time_7 + \beta_{18} FOS_{ij} * time_{14} + \zeta_{ij} - \kappa_s \end{split}$$

 RUX_{ij} : dummy variable for treatment ($RUX_{ij} = 0$ or 1) for participant i in jth site FOS_{ij} : dummy variable for treatment ($FOS_{ij} = 0$ or 1) for participant i in jth site WHO_{ij}^0 : dummy variable for baseline WHO COVID-19 value for participant i in jth site ($WHO_{ij} = 0$ or 1 where 0 indicates score of 3 and 1 indicates score of 4)

 AGE_{ij}^0 : dummy variable for age-group ($AGE_{ij} = 0$ or 1 where 0 indicates < 65 years and 1 indicates \geq 65) for participant i

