3.2.4 Length of stay

The time to discharge will be summarised by treatment arm using a Kaplan-Meier plot with extended at risk tables, detailing the numbers at risk, censored and discharged at each discrete time point, censoring at the day 28 visit. Withdrawals and deaths will be censored at the date of occurrence. In addition, summaries (means (SD) and median (IQR)) of length of stay will be tabulated amongst those that do not withdraw or die.

In addition, a Cox proportional hazards model will be used to estimate the hazard ratio of time to discharge between intervention arms with age (<65 or ≥65), site and receipt of known effective treatments dexamethasone and/or tociluzimab and vaccination status at the time of or prior to randomisation into MATIS included as covariates.

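### The Cox model for time to discharge (SAP 3.2.4) leaves out baseline WHO score, which the main binary and ordinal efficacy models include; the test stays valid, but precision may be lost at no gain

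*SAP*

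**What the plan says.** SAP 3.2.4 estimates a hazard ratio for time to discharge from a Cox model whose covariates are age group, "site and receipt of known effective treatments dexamethasone and/or tociluzimab and vaccination status". Follow-up is censored at day 28. Baseline WHO score is not in the list, and no other section adds it or explains its absence.

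Elsewhere the SAP does adjust for it:

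- **Stage 2 primary model (3.1.3):** "as the outcome and treatment group, baseline WHO COVID-19 score (3 or 4), age" and further covariates.
- **Severe disease within 28 days (3.2.1) and component outcomes (3.2.3):** both reuse the 3.1.3 model.
- **Ordinal model (3.2.2):** "time-by-treatment arm interaction, baseline WHO COVID-19 score (3 or 4".

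The general rules ask for less. Protocol 4.2 wants time to discharge "modelled using a proportional hazards time-to-event model adjusted for randomisation stratification variables". SAP 1.8 says "All regression analysis will include adjustment for age group" and site where appropriate. Those two factors are also the only stratification factors (Protocol 6.2, SAP 1.6).

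The score separates patients with no oxygen (3) from those on "Oxygen by mask or nasal prongs" (4), according to Table 1 of the protocol.

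**The concern.** Reducing the duration of admission is a stated secondary objective (Protocol 2.2). Whether a patient needs oxygen at entry plausibly bears on when they go home, and the plan itself treats the score as prognostic by putting it in the primary model and naming severity as a subgroup factor (Protocol 4.2). In a Cox model, leaving out a baseline predictor has two costs when there is a true effect. The treatment hazard ratio moves towards 1, and the chance that its confidence interval excludes 1 falls. Because randomisation is not stratified by the score, a chance difference in severity between arms would also go straight into the estimate.

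**Working it through.** **The plan's own figures.** The documents give no power, expected hazard ratio or event count for time to discharge, so there is nothing to reproduce on this outcome. The primary design does reproduce. With 5% missing, 57 × 0.95 = 54.15 and 152 × 0.95 = 144.4 per arm are evaluable. For 50% vs 30%, SE = √[(0.25 + 0.21)/n]. The joint chance of passing one-sided 0.25 and then 0.027, with correlation √(54.15/144.4) = 0.61, is 90.0%, against the stated 90%. The point made here does not touch that figure.

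**Inputs for time to discharge.** From the documents: 152 per arm, cut-off at day 28, 95% intervals. Assumed: true discharge HR 1.35; 50–70% of patients at grade 4; discharge HR for grade 4 vs 3 of 0.67, 0.5 or 0.33; exponential discharge times at 0.12 per day; light random censoring. Power means the 95% interval excludes 1 (two-sided 5%), since the SAP sets no threshold for this outcome.

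**Simulation, with and without the score (2,000 trials per setting).** Share of log HR lost = 1 − ln(HR without)/ln(1.35); for example 1 − 0.278/0.300 = 7%. HR and power are from fits without dexamethasone over 50–70% at grade 4. The two loss columns are for 60% at grade 4.

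| Grade 4 vs 3 HR (assumed) | Mean HR without score | Log HR lost | Power without | Power with | Loss, dexamethasone ignored | Loss, dexamethasone in the model and tracking oxygen |
|---|---|---|---|---|---|---|
| 0.67 | 1.34 | 2% | 68% | 71% | about 3 points | 1–3 points |
| 0.5 | 1.32 | 7% | 63% | 70–71% | about 7 points | 2–7 points |
| 0.33 | 1.29 | 15% | 54–57% | 69% | about 13 points | 4–11 points |

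The last column matters because 3.2.4 does include dexamethasone. It assumes roughly 90–95% use at grade 4 and 10–40% at grade 3.

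**Second set of assumptions.** True HR 1.4, an age effect in both fits, median stay about 9 days, 50–85% at grade 4, 1,000 trials per setting (Monte Carlo error about 1.5 points). Score 3 vs 4 discharge HRs of 1.5, 2 and 3 give losses of 1–3, 2–6 and 6–16 points. With dexamethasone as a proxy and 70% at grade 4, the losses are about 0–8 points. As a check on the fits with the score, Schoenfeld's formula with 267 events gives √(267/4) × ln 1.4 − 1.96 = 0.79, so power is about 78.5%. The matching simulated values were 77–81%.

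**Under no effect.** At a true HR of 1.0 the mean HR without the score is 0.99–1.00 and the rejection rate about 4–6%, much the same as with it.

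**Chance imbalance.** With 60% at grade 4, the SD of the between-arm difference is √(2 × 0.6 × 0.4/152) = 5.6 points, so a gap of 1.96 × 5.6 = 11 points lies within the 95% range. With a grade HR of 0.5, to first order, that gap moves the log HR by 0.11 × 0.693 = 0.076, or about 8% on the HR.

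**The case against.** Several points on the other side stand.

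- **No rule is broken.** The protocol asks only for the stratification variables, and 3.2.4 meets that and adds treatments and vaccination. A reader might infer a departure from the protocol; there is none. But since the SAP already goes beyond that minimum, the minimum does not explain leaving severity out.
- **It is not bias in the usual sense.** A reader might take a hazard ratio nearer 1 to mean a confounded or invalid analysis. The score is measured before randomisation, so leaving it out causes no systematic confounding. The shift is non-collapsibility: without the score, the model estimates a hazard ratio averaged over severity, which is a legitimate target.
- **It is not the only comparative estimate.** Protocol 4.2 also specifies a log-rank event rate ratio with a confidence interval. That stands, though this second estimate is not adjusted for the score either.
- **Dexamethasone may stand in for oxygen use.** If so, the loss shrinks, as the last column of the table shows. If nearly everyone receives it, it says little about severity. The documents do not give its use by grade.
- **The score is not in every model.** The laboratory models (SAP 3.2.5) omit it too, but they adjust for the baseline value of the marker being analysed. The discharge model has no baseline severity measure.

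**Conclusion.** The omission is real, unexplained and out of line with the SAP's primary, 28-day, ordinal and component models. Its consequence is lost precision and a hazard ratio nearer 1 if a treatment works, not an invalid test. At an assumed true HR of 1.35 with 60% at grade 4, the loss runs from about 1–3 points of power when the score is weakly prognostic to 4–11 points when it is strong and dexamethasone tracks oxygen. It reaches about 13 points when dexamethasone is ignored. The discharge rates by grade, the grade split, the treatment effect and dexamethasone use by grade are all assumptions, so the direction is firm and the size is not. It would be tempting to read the upper figures as the expected loss; the documents do not support that, because they do not show how strongly the score predicts discharge. The point concerns one secondary outcome with no stated power or threshold, and leaves the primary analysis untouched.

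**What to change.** Add baseline WHO score (3 vs 4) to the Cox covariates in SAP 3.2.4. The cost is one covariate and one line of text. The score is already needed for eligibility (Protocol 5.2) and for the primary model, so no new data are required. Paxlovid and molnupiravir are also in the primary model and absent from this one; the same edit could say whether that is intended.

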3.2.5 Continuous laboratory values

For inflammatory markers of CRP, LDH, ferritin, D-dimer and serum creatinine levels a linear mixed effect model will be used to estimate the mean difference in values between intervention arms (RUX and FOS) and SOC at each follow-up visit (day 1, day 7 and day 14). Participants will be included as a random intercept with fixed effects for time, time-by-treatment arm interaction and baseline values. Stratification variables age and site, plus receipt of known effective treatments dexamethasone and/or tociluzimab, prior vaccination against COVID-19, and receipt of paxlovid and/or molnupiravir at the time of or prior to randomisation into MATIS will also be included as fixed effects. Baseline adjusted treatment group differences with 95% confidence intervals will be presented for each time-point.

For example for CRP the model to be fitted to estimate the treatment effect at each visit up to day 14 will be:

$$\begin{split} Y_{ijt} = \ \beta_0 + \ \beta_1 R U X_{ij} + \ \beta_2 F O S_{ij} + \ \beta_3 C R P_{ij}^0 + \ \beta_4 A G E_{ij}^0 + \ \beta_5 D E X_{ij}^0 \\ + \ \beta_6 T O C_{ij}^0 + \ \beta_7 V A C_{ij}^0 + \ \beta_8 P A X_{ij}^0 + \ \beta_9 M O L_{ij}^0 \ \beta_{10} time_7 \\ + \ \beta_{11} time_{14} + \ \beta_{12} R U X_{ij} * time_7 + \ \beta_{13} R U X_{ij} * time_{14} \\ + \ \beta_{14} F O S_{ij} * time_7 + \ \beta_{15} F O S_{ij} * time_{14} + \ \beta_{16} S I T E_1 \\ + \ \beta_{17} S I T E_2 + \dots + \ \beta_{18} S I T E_{j-1} + b_{1,i} + e_{it} \end{split}$$

for

t = 1 to 3 time points (day 1, 7 and 14), i = 1 to 30 participants

 RUX_{ij} : dummy variable for treatment ($RUX_{ij} = 0 \text{ or } 1$) for participant i

 FOX_{ij} : dummy variable for treatment ($FOS_{ij} = 0 \text{ or } 1$) for participant i

 CRP_{ij}^{0} : baseline CRP value for participant i

 DEX_{ij}^0 : dummy variable for receipt of dexamethasone at the time of or prior to randomisation (includes day of randomisation or one day post randomisation) ($DEX_{ij} = 0 \text{ or } 1$) for participant i TOC_{ij}^0 : dummy variable for receipt of tociluzimab at the time of or prior to randomisation (includes day of randomisation or one day post randomisation) ($TOC_{ij} = 0 \text{ or } 1$) for participant i VAC_{ij}^0 : dummy variable for prior vaccination against COVID-19 at the time of or prior to randomisation (includes day of randomisation or one day post randomisation) ($VAC_{ij} = 0 \text{ or } 1$) for participant i

 PAX_{ij}^0 : dummy variable for receipt of paxlovid at the time of or prior to randomisation (includes day of randomisation or one day post randomisation) ($PAX_{ij} = 0$ or 1) for participant i

 MOL_{ij}^0 : dummy variable for receipt of molnupiravir at the time of or prior to randomisation (includes day of randomisation or one day post randomisation) ($MOL_{ij} = 0$ or 1) for participant i $time_x$: dummy variable for time (= 0 or 1) at time point x days. Day 1 is represented by $time_7 = 0$ and $time_{14} = 0$

Site_i: dummy variable for each of the jth sites

$$b_{1,i} \sim N(0, \sigma_{b1}^2), e_{it} \sim N(0, \sigma_e^2)$$

Where $b_{1,i}$ is the random intercept at the participant level. Each of $b_{1,i}$ and e_{it} are assumed to follow normal distributions. An unstructured covariance matrix will be used and the model will be fitted using restricted maximum likelihood (REML). This model makes assumptions about random effects distributions, correlation structures and residuals, which will all be investigated. If the model fails to converge model estimates will not be presented.

The above will be repeated for each inflammatory marker up to day 14 and additionally up to day 28.

References

- 2. Siddiqui O. Statistical methods to analyze adverse events data of randomized clinical trials. *Journal of Biopharmaceutical Statistics* 2009; 19: 889-899. DOI: http://dx.doi.org/10.1080/10543400903105463.
- 4. White IR, Royston P and Wood AM. Multiple imputation using chained equations: Issues and guidance for practice. *Statistics in Medicine* 2011; 30: 377-399. DOI: https://doi.org/10.1002/sim.4067.
- 5. Kahan BC. Accounting for centre-effects in multicentre trials with a binary outcome when, why, and how? *BMC Medical Research Methodology* 2014; 14: 20. DOI: 10.1186/1471-2288-14-20.
- 6. Kahan BC and Morris TP. Improper analysis of trials randomised using stratified blocks or minimisation. *Stat Med* 2012; 31: 328-340. 2011/12/06. DOI: 10.1002/sim.4431.

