#### 7.1 INTERIM ANALYSIS TO GUIDE DOSING REGIMEN

There is no prior evidence with which to base particular dosing regimens for RUX or FOS for the treatment of COVID-19 pneumonia. After the first 10 patients have been recruited in each arm, an interim analysis will therefore be conducted to test whether a mean 25% decrease in CRP (an inflammatory biomarker) has been achieved in each of the treatment arms compared to SOC at day 14. This analysis will inform a recommendation by the DMC to consider dose escalation for subsequent patients. In the event of that the dosing regimen is changed for subsequent patients, all patients will be included in the final analysis of the primary outcome, but a sensitivity analysis will be performed that excludes patients treated with the prior dosing.

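### SAP 3.2.5 analyses five blood markers as untransformed mean differences, with an ambiguous covariance structure, no named remedy for poor fit, and no model estimate if the fit fails

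*SAP*

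**What the plan says.** SAP 3.2.5 covers CRP, LDH, ferritin, D-dimer and serum creatinine, which SAP 1.1.3 lists as secondary outcomes. It states that "a linear mixed effect model will be used to estimate the mean difference in values between intervention arms (RUX and FOS) and SOC" at days 1, 7 and 14. On structure: "Participants will be included as a random intercept with fixed effects for time, time-by-treatment arm interaction and baseline values". The printed equation has one participant intercept with a single variance and one residual variance common to all visits. The text then adds: "An unstructured covariance matrix will be used and the model will be fitted using restricted maximum likelihood (REML". It does not say whether this refers to the residuals or to the random effects.

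On checking: "This model makes assumptions about random effects distributions, correlation structures and residuals, which will all be investigated". No action is named if a check fails. On non-convergence: "If the model fails to converge model estimates will not be presented". On follow-up: "The above will be repeated for each inflammatory marker up to day 14 and additionally up to day 28".

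Neither document mentions a log transformation or a ratio of geometric means for these markers. SAP 2.7 reports mean (SD) and median (IQR) of the same five markers by arm over time. SAP 2.8 plans a further mixed model for blood measurements, also as a mean difference, and an abnormal/normal analysis at days 14 and 28.

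**The concern.** Concentration-type markers are positive and often right-skewed, with spread that grows with level. On the raw scale a few very high values then dominate the mean and widen the interval. If levels fall as patients recover, the raw variance also changes between visits, whereas the printed equation holds it constant.

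The plan will look at residuals and correlation structure but does not say what follows, so any remedy would be chosen after seeing the data. The only pre-specified response to a failed fit is to show no model estimate. At stake are the precision of five secondary comparisons, and the validity of their standard errors if levels change over time.

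**Working it through.** **No plan figure to reproduce.** The documents give no SD, target effect or power for any marker. From the plan: 152 per arm (SAP 1.5.2), 95% intervals (SAP 1.8), and three visits, or four with day 28 (SAP 3.2.5). Distribution, log-SD, correlations and medians below are assumptions.

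**1. Covariance parameters.** An unstructured residual matrix over T visits has T(T+1)/2 parameters.
- T = 3: 6; with a random intercept, 7.
- T = 4: 10; with a random intercept, 11.

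Under the residual reading, one parameter cannot be identified. Under the random-effects reading, one intercept gives a 1×1 matrix, so the word adds nothing and the model has two variance parameters: one for the intercept and one for the residuals.

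**2. Information lost on the raw scale at one visit.** For a lognormal marker with log-SD s, a small log-scale shift δ moves the raw mean by δ × mean, and the squared coefficient of variation is exp(s²) − 1. Relative efficiency of raw to log is therefore s²/(exp(s²) − 1).

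| log-SD | calculation | efficiency | interval width, raw vs log (1/√efficiency) |
|---|---|---|---|
| 0.3 | 0.09/0.094 | 0.96 | 1.02 |
| 0.6 | 0.36/0.433 | 0.83 | 1.10 |
| 0.8 | 0.64/0.896 | 0.71 | 1.18 |
| 1.0 | 1.00/1.718 | 0.58 | 1.31 |
| 1.2 | 1.44/3.221 | 0.45 | 1.50 |

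At log-SD 1.0 the raw analysis of 152 patients per arm is worth a log analysis of about 152 × 0.58 = 88 per arm.

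A simulated single-visit ANCOVA (152 per arm, true ratio 0.75, baseline correlation 0.5, two-sided 0.05) agrees in direction. Power raw against log was 100% and 100% at log-SD 0.3, 99% and 100% at 0.6, 84% and 96% at 0.8, 57% and 82% at 1.0, and 38% and 68% at 1.2. With no effect, raw rejection stayed at 4% to 5%, so at a single visit the loss is of precision, not validity.

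**3. One common variance when levels fall.** Suppose log-SD is the same at each visit, so raw SD is proportional to the median, and the medians are 90, 40 and 15 at days 1, 7 and 14. Relative variances are 8100, 1600 and 225. The random-intercept model estimates roughly their average, 9925/3 = 3308, whose root is 57.5. Reported over true standard error is then:
- day 1: 57.5/90 = 0.64
- day 7: 57.5/40 = 1.44
- day 14: 57.5/15 = 3.83

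With no effect, a nominal 5% test rejects with probability 2[1 − Φ(1.96 × ratio)]: about 21%, 0.5% and 0%.

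A milder fall (90, 60, 40) gives a mean variance of 13300/3 = 4433, root 66.6, ratios 0.74, 1.11 and 1.66, and rejection of about 15%, 3% and 0.1%. With flat levels and equal spread the ratios are 1 and this problem disappears.

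This arithmetic ignores the baseline covariate. Simulating the printed model with it, and with baseline median 100, gave:
- **Constant correlation 0.5 (log-SD 0.3 to 1.0):** with no effect, raw rejection was 19% to 23% at day 1 and 0% at day 14, against 4% to 6% on the log scale.
- **Correlation falling with time between visits (log-SD 1.0):** with no effect, raw rejection was 16.5%, 2.0% and 0.1% at days 1, 7 and 14, against 1.0%, 5.4% and 8.4% on the log scale. With a true ratio of 0.75 at days 7 and 14, day-14 rejection was 0.4% raw and 83% log.

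So logging removes most of the distortion, but not the part due to correlations that differ between pairs of visits. That part needs the unstructured residual matrix.

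**The case against.** **The printed model can be fitted.** A reader might infer that SAP 3.2.5 specifies an unidentifiable model. That follows only if *unstructured* describes the residuals. The equation, with one residual variance, fits the other reading, under which the phrase is merely redundant. This stands: the point is ambiguity, not proven conflict. The equation's reading, however, is the one that carries the equal-variance assumption in step 3.

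**Little is withheld.** A reader might infer that a secondary outcome disappears on non-convergence. Only model estimates are dropped. The summaries in SAP 2.7 and the analyses in 2.8 remain, and nothing in the documents shows how likely failure is. This also stands. But summaries give no adjusted treatment effect, and the 2.8 mixed model is untransformed too.

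**The loss is assumed.** No distribution is documented, and the loss need not be alike across markers. Nothing shows that LDH or creatinine is in the damaging range. This stands, and the size is stated conditionally.

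**The trial's percentage framing does not settle the scale.** Protocol 7.1 speaks of "a mean 25% decrease in CRP", which might suggest that a ratio scale is already implied. It refers to a mean, which is not a ratio of geometric means, and it belongs to the informal dose check, completed in January 2021 under a separate plan. It is not relied on here.

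**Checks are planned.** They are, but without a named consequence they do not pre-specify an analysis.

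**Conclusion.** The point holds in conditional form. Certain from the text: untransformed mean differences, an undefined use of *unstructured*, checks without a named remedy, and no fallback on non-convergence.

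Conditional on lognormal values: about 17%, 29%, 42% and 55% of the information is lost at log-SD 0.6, 0.8, 1.0 and 1.2, with little loss below 0.6. Conditional also on level and spread falling over visits: the common residual variance gives standard errors too small early and too large late, which is a matter of validity and not only of precision. That second effect does not need strong skewness, since it also appeared at log-SD 0.3.

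The documents do not support saying that all five markers lose precision, that the model cannot be fitted, or that a secondary outcome would be lost. The primary analysis and the stopping rule are untouched. It is a cheap improvement that should be made before the final analysis.

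**What to change.** Amend SAP 3.2.5, and carry the scale through to the mixed model in 2.8:

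1. Log-transform outcome and baseline for the skewed markers: at least CRP, ferritin and D-dimer, with LDH and creatinine added if skewed on blinded pooled data. Report ratios of geometric means with 95% confidence intervals.
2. Use an unstructured residual covariance over visits with no random intercept, and change the equation to match.
3. Replace the withholding rule with an ordered fallback: heterogeneous covariance, then compound symmetry, then ANCOVA at each visit. Always report an estimate and state which step was used.
4. Correct the participant index in the equation. It runs to 30, the size of the informal interim analysis.

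The cost is SAP wording only; no extra data are needed. It is not free: results become ratios rather than differences in units, which changes the quantity estimated; values below detection need a fixed rule; and four visits need 10 covariance parameters instead of 2, which is why the fallback order is required.
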